#### **9.10 OFF STUDY CRITERIA**

- Completion of the 5-year follow-up
- The subject voluntarily withdraws
- The cerclage procedure fails and no implant is left behind, after the first 30 day assessment
- Significant subject non-compliance with follow-up visits, despite repeated site Principal Investigator effort to assure compliance including telephone encouragement and registered letter reminders if necessary.
- Death

Confirmation of survival will be sought from all subjects, even after they voluntarily withdraw, by contacting their physicians, the social security death index, and the subjects themselves.

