| Blood tests (see below)   |                       | X                     |             | X         | X X X          |                        |                           |                |                |                |
| Vital signs and in-person visit   |                       | X                     |             |           | X X X          |                        |                           |                |                |                |
| Cardiac CT contrast-enhanced gated dynamic (Baseline may be up to 6 months old) | Screening or baseline | Screening or baseline | Inpatient * | 30-90d*   | X X            |                        |                           |                |                |                |
| Transesophageal echocardiogram. May be omitted day 0 with SEC concurrence       | Screening or baseline | Screening or baseline | X           |           |                |                        |                           |                |                |                |
| Transcatheter Mitral Cerclage Annuloplasty                                      |                       |                       | X           |           |                |                        |                           |                |                |                |
| Transthoracic echocardiogram (TTE). Baseline may be up to 3 months old.         | Screening or baseline | Screening or baseline |             | X X X X X |                |                        |                           |                |                |                |
| ECG   |                       | X                     |             | X X X X X |                |                        |                           |                |                |                |
| Adverse event assessment  |                       |                       | X X         | X X X X X |                |                        |                           |                |                |                |

|  | Screening ± 6 wks | Baseline ± 6 wks | Day 0 | Inpatient | 30 d (±14d) FU | 6 mo (± 1 mo) (range) FU | 12 mo (± 1 mo) (range) FU | 2 yrs (± 1 mo) (range) | 3 yrs (± 1 mo) | 4 yrs (± 1 mo) | 5 yrs (± 1 mo) |
|--|-------------------|------------------|-------|-----------|----------------|--------------------------|---------------------------|------------------------|----------------|----------------|----------------|

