| Vital status, assessment of SAE and SADE, & clinical echo or echo report. Phone call and review of records from primary physician are acceptable |                   |                  |       |           |                |                          |                           | X                      | X              | X              | X              |
| OPTIONAL: Exercise echocardiogram  |                   |                  | X     |           | X              | X                        | X                         |                        |                |                |                |
| OPTIONAL: Cardiopulmonary Exercise Test (CPEx)   |                   |                  | X     |           | X              | X                        | X                         |                        |                |                |                |

\* follow-up contrast-CT scans may be postponed or omitted as required by patient renal function in written coordination with the sponsor representative.

Subjects would receive continuing care from their primary physicians with consultant input as requested from the structural heart disease program.

For subjects who die, necropsy evaluation is requested to examine the heart at NIH.

In Amendment C, an additional follow-up CT was added at 30-90 days.

In Amendment F, additional 6MWT, KCCQ, and proBNP tests were added at 6 months.

In Amendment G, assessment of and reporting of SAE and SADE is required for long term follow-up.

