### **10.2.3 Adverse Event Reporting**

Adverse event recording will start on Day (0) of the Transcatheter Mitral Cerclage Annuloplasty procedure and will continue through the 12 month Follow Up. Assessment, recording and reporting of serious adverse events (SAE) and serious adverse device effects (SADE) will continue at annual visits thereafter.

New events or conditions present at baseline that increase in severity will be recorded and evaluated and reported on the case report form. Once the subject has completed the 30 day follow up, only serious adverse events (SAE), serious adverse device effects (SADE), unanticipated device effects (UADE) and unanticipated problems (UP) will be reported to the Sponsor . It is the responsibility of the site Principal Investigator to report adverse events and adverse device effects to the IRB of record, to the study sponsor, and to other regulatory bodies according to their reporting requirements. Monitoring visits will be conducted by the Sponsor to review source documentation, and accuracy and completion of the adverse event case report forms.

Section 5.4.1 enumerates blood tests that are monitored for adverse events. No other blood test are reported as adverse events.

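### Off-study rule for visit non-compliance stops non-fatal SAE/SADE follow-up in subjects who have not withdrawn consent, against sections 5.4 and 10.2.3

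*Combined protocol and SAP*

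**What the plan says.** All references are to the combined protocol and SAP.

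- **Section 9.10 (off-study criteria)** lists voluntary withdrawal and, as a separate item, "Significant subject non-compliance with follow-up visits, despite repeated site Principal Investigator effort to assure compliance"; that effort includes phone calls and, if needed, registered letters. For what happens next it says: "Confirmation of survival will be sought from all subjects, even after they voluntarily withdraw, by contacting their physicians", with the death index and the subjects themselves as further sources. It names no other data collection after a subject goes off study.
- **Section 5.4 (schedule)** has a long-term row for vital status, SAE, SADE and a clinical echo or its report, marked at 2, 3, 4 and 5 years. For that row, "Phone call and review of records from primary physician are acceptable". The notes below the table say that, since Amendment G, "assessment of and reporting of SAE and SADE is required for long term follow-up".
- **Section 5.4, earlier visits:** the row "Vital signs and in-person visit" is marked at baseline and three follow-up columns. The table is broken in the extracted text; I read these as 30 days, 6 months and 12 months.
- **Section 10.2.3** has adverse events recorded from the procedure to 12 months, and then: "Assessment, recording and reporting of serious adverse events (SAE) and serious adverse device effects (SADE) will continue at annual visits thereafter".
- **Section 9.2** defines intention-to-treat by an attempted or initiated procedure. It gives no rule for counting subjects who have gone off study. Section 13.5 asks only that missing data be explained on the case report form.

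**The concern.** Non-compliance is listed apart from withdrawal, so it applies to people who have not withdrawn consent. As written, such a person moves from full follow-up to a survival check. A subject removed during year 1 also loses the year 2 to 5 SAE/SADE contacts, which need no visit. The physicians and the subject are still to be contacted about survival, and these are the sources section 5.4 accepts for SAE and SADE. The contact is planned; the safety question is not.

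This matters because the stated objective is feasibility and safety and the implant is permanent. Several harms of interest appear late and need not be fatal. Section 9.5 lists device fracture, migration, thrombosis and device-related infection. Appendix A names erosion, lock failure and later return of regurgitation, and relies partly on serial imaging and continued observation to detect them. With about 30 subjects and a descriptive analysis built on case narratives, one unseen device failure changes the picture. If those who stop attending are sicker than the rest, the reported late rates would be too low.

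**Working it through.** **1. Do the sections agree?**

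| Question | 9.10 | 5.4 and 10.2.3 |
|---|---|---|
| Non-fatal SAE/SADE to 5 years? | Not named once off study | Required |
| Sources | Physicians, death index, subjects (survival only) | Phone call and physician records accepted, years 2 to 5 |
| Consent still in force? | Not considered | No exception for non-compliance |

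No section moves a non-compliant subject to the phone and record route. The conflict is real for a subject removed before year 2.

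**2. Which results are exposed?** Technical success is fixed when the subject leaves the catheterization laboratory (9.3), so it cannot change. Procedural success (9.4), the mortality stopping rule (9.9) and the cohort reports to FDA (10.2.5) use 30-day data. At most one scheduled post-discharge visit has been missed by then, and survival is sought in any case, so these hardly change. What remains is the 6-month, 12-month and 2- to 5-year safety and exploratory results.

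**3. Size.** There is no stated figure to reproduce. Section 9.1 calls the sample size of 30 arbitrary and sets no acceptance criterion; section 7.0 expects high retention without a rate. Losses and risk ratios below are therefore assumptions. I also take all 30 as carrying an implant, in line with section 9.2, which expects the attempted and completed sets to coincide.

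With n = 30, L subjects lost and x events seen in the others:
- rate among those followed = x/(n − L);
- possible proportion in all 30 = x/n to (x + L)/n.

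*Extreme bound, x = 3, L = 3:* seen 3/27 = 11.1%; possible 3/30 = 10.0% to 6/30 = 20.0%. Each lost subject widens the range by 1/30 = 3.3 percentage points.

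*Varying L, x = 2:* lower limit 2/30 = 6.7%; upper limit 3/30 = 10.0% (L = 1), 5/30 = 16.7% (L = 3), 7/30 = 23.3% (L = 5).

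*Moderate case, L = 3:* retained subjects have a 10% risk and lost subjects r times that. Overall rate = (0.10 × 27 + 0.10 × r × 3)/30:
- r = 1: 10.0%
- r = 2: (2.7 + 0.6)/30 = 11.0%
- r = 3: (2.7 + 0.9)/30 = 12.0%

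*Precision alone:* with zero events the one-sided 95% upper limit is 1 − 0.05^(1/n), which gives 9.5% (n = 30), 10.5% (n = 27) and 11.7% (n = 24).

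The loss of precision is small. The bias is 1 to 2 points in the moderate case and larger only if most of those lost had events.

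**The case against.** The strongest reply has five parts.

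1. **The trigger is demanding.** A reader might infer that any missed visit ends participation. It does not: non-compliance must be significant and persist after repeated phone and letter contact. Some subjects who reach that point will be unreachable or unwilling, and a further call will fail. This stands, but their physicians' records may still be available.
2. **Remote follow-up is not already accepted throughout.** The phone and records row covers years 2 to 5 only, and there a call is itself compliant follow-up. The criterion therefore bites mainly in year 1, where in-person visits are scheduled. This stands: using remote SAE/SADE follow-up in year 1 is a proposal, not current practice.
3. **Selective loss is not shown.** One might conclude that harms are lost in the sickest subjects. The documents give no evidence of this and expect high retention. It is a plausible risk only.
4. **The denominator is not stated to shrink.** Under the section 9.2 definition, all attempted procedures stay in the intention-to-treat set and events recorded before exit are kept. So 3/27 is an assumed way of reporting, and 20.0% requires every lost subject to have had an event.
5. **Survival-only is read from silence.** Section 9.10 does not forbid recording an SAE that a physician mentions, and the fact of death is not lost. That is correct, but it does not require anyone to ask. Nor does it provide for the information on relatedness that section 9.6 needs when first-year deaths are adjudicated.

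These points limit the size and reach of the problem. None removes the conflict between the sections.

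**Conclusion.** The point holds as a gap between section 9.10 and sections 5.4 and 10.2.3. For a consenting subject taken off study for persistent visit non-compliance, the plan names only survival confirmation, while elsewhere it requires SAE/SADE assessment to 5 years. Non-fatal late device harms may be missed in those subjects.

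The effect is confined to 6-month to 5-year safety and exploratory results. The size is unknown because no loss rate is given. The range of 10.0% to 20.0% is an extreme bound for 3 assumed losses out of 30; if lost subjects carry two to three times a 10% risk, the overall rate is 11% to 12%. The documents do not support saying that harms are in fact lost selectively, that deaths are lost, or that the main results are biased. The change is worth making because it is cheap and protects the safety aim, not because the study fails without it.

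**What to change.** - **Section 9.10:** replace the non-compliance criterion with a status of having stopped study visits. Such subjects stay in follow-up for vital status, SAE and SADE by phone and record review until 5 years unless they withdraw consent. Keep the existing survival check after withdrawal.
- **Section 5.4:** state that, for these subjects, the phone and record route also serves for SAE/SADE in year 1. Record the in-person tests they miss as missing assessments, not as study exit.
- **Section 9.2:** keep these subjects in the attempted-procedure denominator. At each time point, report the number not ascertained next to each late safety rate.
- Reconcile sections 9.10, 5.4 and 10.2.3 so that they describe one follow-up path.

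The cost is an amendment to the wording and a few calls or record requests, a method already planned for years 2 to 5 and new only for year 1. Some attempts will fail for unreachable subjects, and remote review will not replace missed imaging or walk tests.

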#### **10.0 ADVERSE EVENT REPORTING**

##### **10.1 DEFINITIONS**

*Adverse events:* Any untoward medical occurrence in a human subject, including any abnormal sign (e.g., abnormal physical exam or laboratory finding), symptom, or disease, temporally associated with the subject's participation in the research, whether or not considered related to the subject's participation in the research.

This will include:

- Expected events related to the subject's disease process during active enrollment in the research protocol and do not directly result from use of the investigational device or study.
- Procedural events directly related to the cardiac catheterization procedure and recovery from the procedure and do not directly result from use of the investigational device.

*Serious Adverse Event (SAE):* A serious adverse event that results in any of the following and NOT directly related to the device. This includes any event that

- Results in death
- Is life-threatening (places the subject at immediate risk of death from the event as it occurs);
- results in in-patient hospitalization or prolongation of existing hospitalization;
- results in a persistent or significant incapacity;
- results in a congenital anomaly/birth defect (not relevant to this study); or
- based upon appropriate medical judgment, may jeopardize the subject's health and may require medical or surgical intervention to prevent one of the other outcomes listed in this definition.

*Adverse Device Effect (ADE):* Any untoward or unintended response to a medical device. This definition includes any event resulting from insufficiencies or inadequacies in the instructions for use or the deployment of the device or any event that is a result of user error.

During this clinical investigation an event should be considered related to the device when it is the result of:

- Transcatheter Mitral Cerclage Annuloplasty procedure
- Transcatheter Mitral Cerclage Annuloplasty device

An event will be considered NOT related to the Transcatheter Mitral Cerclage Annuloplasty procedure when it is the result of a pre-existing medical condition.

*Anticipated Adverse Device Effects (AADEs):* An AADE is an adverse event with a reasonable possibility that the device or procedure caused or contributed to the event. The following AADEs are considered anticipated based on judgement and clinical experience:

- Death
- Cardiac arrhythmia including ventricular tachycardia, ventricular fibrillation, supraventricular tachycardia, and atrial fibrillation and including cardiac arrest
- Cardiopulmonary resuscitation (CPR) in response to cardiac arrhythmia, cardiac arrest, or cardiogenic shock
- Anaphylactic or toxic reaction to anesthesia, medications, or contrast media, or device materials
- Hypersensitivity or immune reaction to the test article(s) or their components
- Complications of vascular access including bleeding (hemorrhage), fistula, dissection, pseudoaneurysm, retroperitoneal hematoma, pneumothorax, hemothorax, site hematoma or bruising and requiring transcatheter or surgical repair or further medical evaluation or management.
- Conduction system injury including atrio-ventricular conduction block, high-degree atrio-ventricular block, partial and complete bundle branch block, requiring CPR or temporary or permanent pacemaker. At present we believe there is a high chance of needing a pacemaker after the cerclage procedure.
- Coronary artery compression which may cause angina, myocardial ischemia, myocardial infarction, or ventricular arrhythmia, caused either by the cerclage device or by coronary arteriography during or after implantation, and that may require percutaneous or surgical intervention
- Embolization of air, thrombus, or debris to coronary arteries, brain, limbs, or viscera causing myocardial infarction, stroke, transient ischemic attack, etc
- Transcatheter Mitral Cerclage Annuloplasty device failure including failure to traverse, to deliver, to position, or to lock catheters or guidewires
- Malposition, embolization, dislocation, migration, or deployment in an unintended location of the cerclage device or its components, or surgical retrieval
- Myocardial or coronary vein perforation during the implantation procedure causing pericardial effusion or tamponade, including requiring percutaneous or surgical intervention.
- Bleeding (hemorrhage) caused by the cerclage implantation procedure apart from vascular access complications, including blood transfusion
- Bleeding (hemorrhage) caused by vascular access for the cerclage implantation procedure, including causing low blood pressure and requiring vasopressor support or requiring blood transfusion
- Anemia requiring blood transfusion, such as from procedural blood loss
- Coronary vein dissection or thrombosis caused by the cerclage implantation procedure
- Mechanical injury to the myocardium or heart valves that may cause elevation of myocardial biomarkers (Troponin) other than myocardial infarction
- Mechanical injury to, or decline in function of, tricuspid or aortic heart valves or subvalvular apparatus causing valve regurgitation including requiring mechanical intervention
- Chest pain
- Cardiogenic shock or hypotension caused by valvular, subvalvular, or myocardial injury during or after cerclage implantation procedure requiring vasopressor support or mechanical circulatory support or other mechanical or surgical intervention

- Myocardial erosion which may cause myocardial perforation, intracardiac shunt, pericardial effusion or tamponade and which may require surgical or transcatheter intervention
- Renal injury or failure, including contrast-induced nephropathy, requiring temporary or permanent hemodialysis or medical treatment
- Volume overload, congestive heart failure, dyspnea, pulmonary edema, or pleural or pericardial effusion from procedure-related volume perturbations
- Congestive heart failure, cardiomyopathy, cardiogenic shock, respiratory failure, BNP elevation
- Narrowing the mitral valve too much, causing a condition called mitral valve stenosis. This can result in lung congestion causing shortness of breath, similar to symptoms of leaky (regurgitant) mitral valve.
- Respiratory failure requiring oxygen or mechanical support or mechanical ventilation
- Endocarditis or endarteritis or sepsis related to the cerclage device
- Venous thrombosis or thromboembolism including deep vein thrombosis, and pulmonary thromboembolism
- Ecchymoses or gastric bleeding related to anti-platelet medications.
- Other infection related to access site or procedure including urinary or pulmonary or sepsis
- Pain including back pain and access site pain and generalized pain
- Low or high blood pressure values, or low or high heart rate values, whether related to anesthesia or not
- Abnormal blood cell tests including hemoglobin, hematocrit, platelets and white blood cells
- Abnormal blood chemistries including creatinine, troponin, and NT-pro-BNP
- Radiation injury including intractable skin injury
- Emergency cardiovascular surgery

***Serious Adverse Device Effect (SADE):*** An adverse effect that may have been or is attributed to the use of the device and produce an injury or illness that is life-threatening, results in permanent impairment or damage to the body, or requires medical or surgical intervention to prevent permanent harm to the body.

***Unanticipated Adverse Device Effect (UADE):*** Any serious adverse effect on health or safety or any life-threatening problem or death caused by, or associated with, a device, if that effect, problem, or death was not previously identified in nature, severity, or degree of incidence in the investigational plan or application (including a supplementary plan or application), or any other unanticipated serious problem associated with a device that relates to the rights, safety, or welfare of subjects (21 CFR 812.3(s)).

***Unanticipated Problem (Up):*** An unanticipated problem is any incident, experience, or outcome that meets ALL of the following criteria:

- Unexpected in terms of nature, severity, or frequency in relation to:
  - a. the research risks that are described in the IRB-approved research protocol and informed consent document, Investigator's Brochure or other study documents, and
  - b. the characteristics of the subject population being studied, and
- Related or possibly related to participation in the research, and
- Suggests that the research places subjects or others at a greater risk of harm (including physical, psychological, economic, or social harm) related to the research than was previously known or expected.

***Unanticipated Problem that is not an Adverse Event:*** An unanticipated problem that does not fit the definition of an adverse event, but which may, in the opinion of the NIH and site Principal Investigators,

involves risk to the subject, affect others in the research study, or significantly impact the integrity of research data. For example, report occurrences of breaches of confidentiality, or accidental destruction of study records.

*Protocol Deviation:* A protocol deviation is any change, divergence, or departure from IRB-approved research protocol.

*Major Deviations* - Deviations from the IRB approved protocol that have, or may have the potential to, negatively impact, the rights, welfare or safety of the subject, or to substantially negatively impact the scientific integrity or validity of the study.

*Minor Deviations* - Deviations that do not have the potential to negatively impact the rights, safety, or welfare of subjects or others, or the scientific integrity or validity of the study.

*Non-compliance:* Failure of investigator(s) to follow the applicable laws, regulations, or institutional policies governing the protection of human subjects in research, or the requirements or determinations of the IRB, whether intentional or not.

Serious non-compliance: Non-compliance, whether intentional or not, that results in harm or otherwise materially compromises the rights, welfare and/or safety of the subject. Non-compliance that materially effects the scientific integrity or validity of the research may be considered serious non-compliance, even if it does not result in direct harm to research subjects.

Continuing non-compliance: A pattern of recurring non-compliance that either has resulted, or, if continued, may result in harm to subjects or otherwise materially compromise the rights, welfare and/or safety of subjects, affect the scientific integrity of the study or validity of the results. The pattern may comprise repetition of the same non-compliant action(s), or different noncompliant events. Such non-compliance may be unintentional (e.g. due to lack of understanding, knowledge, or commitment), or intentional (e.g. due to deliberate choice to ignore or compromise the requirements of any applicable regulation, organizational policy, or determination of the IRB).

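### Hospitalization counts as serious only for events not directly caused by the device, so some device-caused admissions drop out of recording in years 2 to 5; the NIH PI table also lacks a SADE row

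*Combined protocol and SAP*

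**What the plan says.** All references are to the combined protocol and SAP.

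Section 10.1 defines an SAE as "A serious adverse event that results in any of the following and NOT directly related to the device". One of its listed outcomes is that the event "results in in-patient hospitalization or prolongation of existing hospitalization". Both reporting tables in section 10.2.4 repeat the restriction in the label of their SAE row, so it is not a stray phrase.

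An SADE, in the same section, is an effect that is or may be attributed to the device and whose injury or illness "is life-threatening, results in permanent impairment or damage to the body, or requires medical or surgical intervention to prevent permanent harm to the body".

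Section 10.2.3 sets the recording period: "Adverse event recording will start on Day (0) of the Transcatheter Mitral Cerclage Annuloplasty procedure and will continue through the 12 month Follow Up". After that, "Assessment, recording and reporting of serious adverse events (SAE) and serious adverse device effects (SADE) will continue at annual visits thereafter". The last part of the schedule in section 5.4 agrees: the contacts at years 2, 3, 4 and 5 assess SAEs and SADEs, and a note attributes this long-term requirement to Amendment G.

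In section 10.2.4 the site Principal Investigator's table gives SADEs 3 working days, SAEs 5 and anticipated ADEs 7, all to the sponsor. The NIH Principal Investigator's table gives a non-device SAE 14 days to the Clinical Director and has no row for SADEs.

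**The concern.** For a permanent implant whose safety is part of the study objective (section 1.0), the definitions run the wrong way. The same hospital admission is serious if the device did not directly cause it, and may be non-serious if the device did. Up to month 12 this changes labels and reporting times, but the event is still recorded. After month 12 it decides whether the event is recorded at all. Amendment G extended safety follow-up to year 5, and the risk analysis in Appendix A names failures that could appear late, such as erosion, lock failure and returning regurgitation. With 30 treated subjects and a descriptive analysis (sections 9.1 and 9.2), each missed device-caused admission matters to the long-term safety account.

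The missing SADE row is a separate matter. It concerns how quickly the Clinical Director must be told, and not whether the event is recorded.

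**Working it through.** The plan gives no figure to reproduce here. The check sets the definitions, the recording rule and the reporting tables side by side.

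**Step 1: seriousness criteria (section 10.1).** The SAE list has 6 outcomes, one of which (birth defect) is marked not relevant, leaving 5.

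| Outcome | SAE | SADE |
|---|---|---|
| Death | listed | not named, but death has its own row in both reporting tables |
| Life-threatening | listed | listed |
| New or prolonged hospital stay | listed | absent |
| Incapacity | persistent or significant | only as permanent impairment or damage |
| Intervention | to prevent any other listed outcome | only to prevent permanent harm |

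Hospitalization also appears in the grading table of section 10.2.1, but as a description of severity and not as a test of seriousness.

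**Step 2: follow one admission through the definitions.** Suppose that in year 3 a subject is admitted for observation of chest pain directly caused by the device. Assume that it is not life-threatening, leaves no permanent damage and needs no intervention to prevent permanent harm.

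- SAE: no, because it is directly device-related.
- SADE: no, because none of the three criteria is met.
- UADE: not normally. Chest pain is on the anticipated list, which has 1 + 15 + 20 = 36 entries. A listed type qualifies only if its nature, severity or incidence was not previously identified.
- Unanticipated problem: not normally, because the event must be unexpected.

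It remains a non-serious ADE.

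**Step 3: apply the recording rule.** General recording ends at month 12. The four annual contacts at years 2 to 5 (months 12 to 60) cover SAEs and SADEs only, so this admission is outside the rule. If the chest pain had not been device-related, hospitalization would make it an SAE and it would be recorded.

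**Step 4: the NIH Principal Investigator's table (section 10.2.4).** It has 19 rows, and 9 name the Clinical Director.

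| Row | Clinical Director limit |
|---|---|
| Death | 24 hours or 7 days |
| UADE | 7 days |
| Unanticipated problems | 7 days |
| Major deviations | 7 days |
| Serious or continuing non-compliance | 7 days |
| New information | 7 days |
| SAE, non-device | 14 days |
| Minor deviations | 14 days |
| Adverse events | annual summary |

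Eight rows therefore have a limit between 24 hours and 14 days, and one is annual. None is for SADEs, and the anticipated ADE row goes to FDA and the IRB only. An anticipated, non-fatal SADE fits none of the expedited event rows by type. Under this table it reaches the Clinical Director at most through the annual adverse event summary, unless it also counts as new information bearing on willingness to participate.

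**Step 5: what is not touched.** Technical success is measured at exit from the catheterization laboratory (section 9.3). Procedural success is measured at 30 days and carries its own wording of the device effects that count (section 9.4.1). The stopping rule counts 30-day deaths (section 9.9). None depends on the gap.

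**The case against.** The strongest reply is that little escapes. The SAE exclusion applies only to events directly related to the device, so an indirectly related admission can still be an SAE. SADE attribution is broad, and its intervention criterion will catch many admissions. No planned endpoint counts hospitalizations, and the dated exploratory endpoints in section 9.5 stop at 12 months, while all adverse events are still being recorded. The annual call, record review and echo may also bring an event to light. All of this stands and limits the size of the gap, but none of it supplies the missing criterion or places such an admission under the long-term recording rule.

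A reader might infer more than the documents support, in four ways.

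- *That device-related admissions in general are lost in years 2 to 5.* They are not. The loss is confined to those directly caused, of an anticipated type and meeting no SADE criterion.
- *That an SADE could go unnoticed for a year.* The annual summary concerns one line of reporting to the Clinical Director. Sites must tell the sponsor within 3 working days, and the sponsor representative acts for the Office of Clinical Director (section 14.1). The DSMB reviews progress every six months, and the IRB sees SADEs at continuing review (section 9.8).
- *That section 10.2.3 contradicts itself at day 30.* It says "Once the subject has completed the 30 day follow up, only serious adverse events (SAE), serious adverse device effects (SADE", with UADEs and unanticipated problems, go to the sponsor. The broader site duty that follows is qualified by the recipients' own reporting requirements, so the two can be read together. The ADE row in the site table simply lacks a cross-reference.
- *That unclear classification of procedural events widens the gap.* Section 10.1 counts "Procedural events directly related to the cardiac catheterization procedure and recovery from the procedure" among adverse events not directly resulting from the device. It also says "During this clinical investigation an event should be considered related to the device when it is the result of" the cerclage procedure or device. The two statements need reconciling, but index-procedure admissions will mostly fall inside the 12 months when every event is recorded.

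**Conclusion.** The concern holds in a narrow form. Followed as written, the plan omits from year 2 to 5 recording any directly device-caused admission of an anticipated type that meets none of the three SADE criteria, and keeps the same admission when it is unrelated to the device. The number affected is probably small and cannot be estimated from the documents. Separately, an anticipated, non-fatal SADE has no expedited Clinical Director limit, although a non-device SAE has 14 days.

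This rests on reading the SAE restriction literally, which the row labels in both tables support, and on sites applying the definitions as written. It affects the completeness of the long-term safety description, not any primary, secondary or stopping-rule result. It merits correction because the rule records less precisely where the device is the cause.

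**What to change.** - **SADE criteria (section 10.1).** Add new or prolonged hospitalization, and persistent or significant incapacity, so that the criteria match the SAE list. The admission in step 2 would then be an SADE, recorded at the annual contact and reported to the sponsor within 3 working days. At minimum, require device-related admissions to be recorded at the year 2 to 5 contacts.
- **NIH Principal Investigator's table (section 10.2.4).** Add a SADE row with a Clinical Director limit no slower than the 14 days of the SAE row.
- **Minor clarifications.** State whether purely procedural events are classed as SAE or SADE (section 10.1), and cross-refer the day-30 sentence in section 10.2.3 to the ADE row of the site table.

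The cost is wording and one table row, with no added visits. The downside of the full change is that some more peri-procedural device-related events, including prolonged index stays, would become serious and be reported in 3 rather than 7 working days. The number cannot be estimated and may not be trivial, since every subject is admitted and section 10.1 expects frequent pacemaker need. The minimum version avoids most of this.
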